ABSTRACT

Background:

After endotracheal intubation verifying the location of endotracheal tube is of utmost importance. Many methods have been applied but none is perfect. The standard practice is to use auscultation of chest with capnography. Ultrasound machines are now gaining popularity and their access extends from operation theatres, emergency rooms and even many primary health centres. Both capnography and ultrasonography are proven to be safe. This study aims to see if ultrasonography can also be made a routine method of endotracheal tube position confirmation inside operating theatres along with capnography.

Methods:

This was a prospective, observational study conducted at the Tribhuvan University Teaching Hospital (TUTH) and Manmohan Cardiothoracic Vascular and Transplant Center (MCVTC) operating rooms from January 2017 to July 2017. Ethical approval from the Institutional Review Board (IRB) of Institute of Medicine (IOM) and the Department of Anaesthesiology, Maharajgunj Medical College (MMC) was taken. Written informed consent was taken.

ASA I and II patients over 16 years of age were included in this study. Patients with difficult airway and anticipated difficult intubation, respiratory diseases, poor functional status, emergency case, and patients at risk of aspiration were excluded.

The diagnostic characteristics of real-time, suprasternal, transtracheal ultrasonography and capnography were tested by calculating their respective sensitivities, specificities, positive predictive values (PPV), negative predictive values (NPV), accuracies and likelihood ratios. Comparison of time taken for confirmation of endotracheal tube

position from the beginning of laryngoscopy, by ultrasonography versus capnography was done using t-statistics.

The degree of agreement of result between ultrasonography and capnography was tested with kappa statistics.

Results:

Out of the 95 patients studied, 11 had oesophageal intubation (Incidence of 11.57%). The overall accuracy of both ultrasonography and capnography was 96.84%. The sensitivity, specificity, PPV, NPV with their corresponding 95% confidence intervals (CI) for ultrasonography were 97.62% (91.66% - 99.71%), 90.91% (58.72% - 99.77%), 98.80% (92.67% - 99.81%), 83.33% (55.66% - 95.22%) respectively; and that for capnography were 96.43% (89.92% - 99.26%), 100% (71.51% - 100%), 100% (100% - 100%) and 78.57% (54.69% - 91.76%) respectively.

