After confirmation of the endotracheal tube position, true and false positives and negatives were determined for both the methods as depicted in table 1.

Sensitivity, specificity, positive predictive value and negative predictive value, likelihood ratios; for both ultrasonography and capnography were calculated using their corresponding formulas.³⁷ The results were extrapolated into confidence intervals using Clopper-Pearson confidence interval.³⁷

Table 1. Designation of true and false positives and negatives.

Capnography		Ultrasonography	
Tracheal outcome	Oesophageal outcome	Tracheal outcome	Oesophageal outcome
True positive (TP): final position in trachea.	True negative (TN): final position in oesophagus.	True positive (TP): final position in trachea.	True negative (TN): final position in oesophagus.
False positive (FP): final position in oesophagus.	False negative (FN): final position in trachea.	False positive (FP): final position in oesophagus.	False negative (FN): final position in trachea.

Sensitivity = TP / (TP+FN).

Specificity = TN / (TN+FP).

Positive predictive value (PPV) = TP / (TP+FP).

Negative predictive value (NPV) = TN / (TN+FN).

Confidence intervals, CI (at 95 % level of confidence): for example for sensitivity

CI = (Sensitivity + 1.96SE, sensitivity – 1.96SE). Where SE is standard error,

SE for sensitivity = square root of [sensitivity (1 – sensitivity)/(TP+FN)]³⁷

Accuracy = $(TP+TN) / (TP+TN+FP+FN)$.

(TP=True Positive, TN=True Negative, FP=False Positive, FN= False Negative)

Likelihood ratio of a positive test: was given by

$$LR_{+} = \frac{\text{sensitivity}}{1 - \text{specificity}}$$

The positive likelihood ratio values corresponded to different probabilities as follows³⁷:

Table 2. Interpretation of positive likelihood ratio.³⁷

Positive likelihood ratio value	Probability
0	Excluded disease.
> 10	Large change in likelihood (or in other words high probability of any individual having a positive result on using the diagnostic test).
5 – 10	Moderate change in likelihood.
2 – 5	Small change in likelihood.
1	No change.

Likelihood ratio of negative test: was given by

$$LR_{-} = \frac{1 - \text{sensitivity}}{\text{specificity}}$$

The negative likelihood ratio values also corresponded to different probabilities as follows³⁷:

Table 3. Interpretation of negative likelihood ratio.³⁷

Negative likelihood ratio value	Probability
infinity	Excluded normality.

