Among the 95 subjects, the mean age was found out to be 44.24 years with standard deviation of ± 16.18 years, and the median age was 47 years. The youngest patient was of 16 years, and the eldest patient was 85 years old. Most patients were in the age group of 41 to 50 years.

Table 5. Demographic profile according to age.

Mean \pm SD (in yrs)	Median (in yrs)	Maximum (in yrs)	Minimum (in yrs)
44.24 \pm 16.18	47	85	16

(n=number, SD= Standard Deviation, yrs = years)

[figure not shown]

Fig. 9. Distribution of the subjects into different age groups.

Among the 95 subjects, there were 51 females (53.68%) and 44 males (46.32%) in this study.

[figure not shown]

Fig. 10. Sex-wise profile of patients in the study.

The majority of patients were Brahmins (40%), followed by Chhetris (22.10%), Newars (14.70%), Magars (7.36%), and others (15.84%); as shown in figure 11. Others include Rai (4), Bhaisnav (1), Chaudhary (1), Muslim communities (2), Lama (2), Gurung (1), Damai (1), Tamang (2), Thakuri (1) and Sherpa (1).

BMI

The mean body mass index (BMI) of the 95 patients was found to be 23.55 ± 3.58 (mean \pm standard deviation); the median BMI was 23.72 and the inter-quartile range [20.68 - 25.92], all values expressed in kg/m^2 . The summary is shown in table 3 and figure 12.

[figure not shown]

Fig. 11. Distribution of patients as per ethnicity in this study.

Table 6. Average body mass index (BMI) of patients.

	Mean \pm SD	Range	Median	IQR
BMI (kg/m^2)	23.55 \pm 3.58	16.33 - 33.88	23.72	[20.68 - 25.92]

(SD = Standard Deviation, Range = Maximum - minimum values; IQR = Interquartile range)

[figure not shown]

Fig. 12. Frequency of patients according to WHO classification of BMI.

ASA Physical Status

There were 46 ASA I patients and 49 ASA II patients in this study. The clinical conditions in patients with ASA II status are listed below in table 4. Table 4 does not account for the presence of multiple clinical conditions in the patients.

[figure not shown]

Fig. 13. ASA Physical status distribution of patients.

Table 7. Clinical conditions in ASA II patients.

	No. of patients	
	MCTVC	TUTH
Valvular heart disease	8	0
Coronary heart disease	14	1
Vascular disease	6	0
Hypertension	14	6
Diabetes Mellitus	4	1
Hypothyroidism	3	3
Hepatitis C positive	0	1
Central nervous system disease	0	8

Analytical Statistics and Data

Out of the total 95 intubations, there were 11 oesophageal intubations. The incidence of oesophageal intubation was 11.57% in this study.

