Ultrasonography

Ultrasound falsely detected one oesophageal intubation as tracheal, and two tracheal intubations as oesophageal.

Table 8. Distribution of positives and negatives for ultrasonography.

Position showed by Ultrasound	Endotracheal tube position confirmation		Total
	Trachea	Oesophagus	
Trachea (n)	TP = 82	FP = 1	83
Oesophagus (n)	FN = 2	TN = 10	12
Total	84	11	n = 95

(n=no. of patients, TP=True Positives, FP=False Positives, FN=False Negatives, TN=True Negatives)

The sensitivity, specificity, positive predictive value and negative predictive value (with their corresponding 95% confidence intervals in round brackets) were calculated to be 97.62% (91.66% - 99.71%), 90.91% (58.72% - 99.77%), 98.80% (92.67% - 99.81%) and 83.33% (55.66% - 95.22%) respectively. The positive likelihood ratio was 10.74, which suggested a large change in the likelihood of positive result. The negative likelihood ratio was 0.03 which also suggested a large change in the likelihood of negative result. The accuracy of ultrasonography in confirming endotracheal tube placement was 96.84% (92.92% - 100%).

[figure not shown]

Fig. 14. Distribution of positives and negatives for ultrasonography.

Capnography

There were three false negative results given by waveform capnography. There was no false positive result.

Table 9. Distribution of positives and negatives for capnography.

Position showed by waveform capnography	Endotracheal tube position confirmation		Total
	Trachea	Oesophagus	
Trachea (n)	TP = 81	FP = 0	81
Oesophagus (n)	FN = 3	TN = 11	14
Total	84	11	n=95

(n=no. of patients, TP=True Positives, FP=False Positives, FN=False Negatives, TN=True Negatives)

[figure not shown]

Fig. 15. Distribution of positives and negatives for capnography.

The sensitivity, specificity, positive predictive value and negative predictive value (with their corresponding 95% confidence intervals in round brackets) of capnography were calculated to be 96.43% (89.92% - 99.26%), 100% (71.51% - 100%), 100% (100% - 100%) and 78.57% (54.69% - 91.76%) respectively. The positive likelihood ratio was infinity. The negative likelihood ratio was 0.04 which suggested a large change in the likelihood of negative result. The accuracy of capnography in confirming endotracheal tube placement was 96.84% (92.92% - 100%).

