Hence these descriptive variables did not affect the outcome of the study. These variables reflect the demographic profile of the patients served at the academic centres of IOM in Maharajgunj and provide validity to the study. This data could help as reference for researchers who might carry out similar studies in the same centres in future.

Analytical Statistics

The incidence of oesophageal intubation was 11.57% in this study. Reported incidence of oesophageal intubations during elective intubation is less than 2%.^{12,39}

The incidence of oesophageal intubation increases up to 6 - 16 % during in-hospital emergency intubations.^{29,30,39,40}

Ultrasonography

In this study, the sensitivity, specificity, positive predictive value and negative predictive value (with their corresponding 95% confidence intervals) of ultrasonography were calculated to be 97.62% (91.66% - 99.71%), 90.91% (58.72% - 99.77%), 98.80% (92.67% - 99.81%) and 83.33% (55.66% - 95.22%) respectively.

The sensitivity of ultrasonography in this study is comparable to sensitivity reported in the meta-analyses done by Das et al²¹ and Chou et al⁶, which were 98% and 93% respectively. The specificity was 90.91% in this study, which is slightly lower compared to the above mentioned meta-analyses where specificity ranges from 97 to 98%.^{6,21} But the 95% confidence interval of specificity in this study extends from 58.72 to 99.77% which covers the reported specificity 97 to 98% in these meta-analyses. Thus the calculated pretest probabilities of ultrasonography in this study were not different from those reported in literature.

The PPV and NPV of ultrasonography calculated in this study were 98.8% and 83.33% respectively. The PPV of ultrasonography in this study is similar to that found by Adi et al³⁰, Chou et al²⁸, Chintamani et al³⁴ and Nasreen et al³³: the reported PPV ranges from 98 to 100% in these studies. The NPV of ultrasonography has been reported to be: 62.5% by Chintamani et al³⁴, 75% by Adi et al³⁰, 94% by Chou et al²⁸, and 96.77% by Nasreen et al³³. The 95% confidence interval of NPV of ultrasonography in this study was (55.66%- 95.22%), which is comparable to the NPV found by the above mentioned studies.

Ultrasonography had an accuracy of 96.84% in endotracheal tube confirmation in this study. Similar accuracy ranging from 97 to 98% had also been found by previous researchers.^{28,30,33}

There are various ways of using ultrasonography for endotracheal tube confirmation.

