Chintamani et al³⁴ in their study comparing ultrasound and capnography found mean \pm SD time for confirmation by ultrasound to be 12 ± 1.31 secs, and that by capnography to be 8.98 ± 1.04 secs. Their finding of capnography being significantly faster is debatable because they used transtracheal ultrasound at suprasternal level first in transverse view then in longitudinal view, followed also by scanning towards the left side of neck to align the area of oesophagus towards the center of probe. They also have not mentioned the criterion for capnography, whether $ETCO_2$ values were used or not, and the number of waves they counted for a result.

LIMITATIONS

1. This study used both sidestream and mainstream capnographs as per availability at the study sites. Sidestream capnographs have a delay time in reading exhaled CO₂, which does not occur in mainstream capnographs.
2. Different persons (anaesthesia faculties with training in airway ultrasound) performed ultrasound imaging in this study.
3. This study did not see if novice ultrasound operators could also confirm endotracheal tube position by ultrasound imaging earlier than capnography.

CONCLUSION

Ultrasonography and waveform capnography are equally reliable and accurate methods of confirming endotracheal tube position. Confirmation of endotracheal tube position by real-time ultrasonography is faster than capnography independent of the ultrasound operator. The combination of ultrasonography with capnography in practice will help reduce time and increase precision of confirming endotracheal tube position.

RECOMMENDATIONS

- Real-time transtracheal ultrasonography is safe and can be used as an alternate method of confirming endotracheal tube position in operating theatres.
- Using real-time transtracheal ultrasound can help confirm endotracheal tube position earlier than capnography.
- Using real-time transtracheal ultrasound will help avoid manual bag ventilations to confirm endotracheal tube position and can prevent aspiration of gastric contents into lungs in cases of oesophageal intubation.

REFERENCES

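### Calling ultrasonography and capnography 'equally' reliable and accurate is not supported: neither the tied accuracy nor overlapping intervals on 11 oesophageal tubes shows equality

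*Combined protocol and SAP*

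**What the plan says.** The Methodology section defines accuracy as ("TP+TN) / (TP+TN+FP+FN"), so every error counts once. The Abstract's Results give the outcome for the two methods: "The overall accuracy of both ultrasonography and capnography was 96.84"%.

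The errors behind that figure are set out in the Results. On the case mix: "Out of the total 95 intubations, there were 11 oesophageal intubations". On ultrasound: "Ultrasound falsely detected one oesophageal intubation as tracheal, and two tracheal intubations as oesophageal". On capnography: "There were three false negative results given by waveform capnography. There was no false positive result".

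The Discussion, under Ultrasonography vs Capnography, allows that capnography looked more specific. It then treats sensitivity, specificity, PPV and NPV as comparable because the confidence intervals do not separate the methods, and calls the methods equally reliable. The same part says that combining the methods raised precision, which it equates with accuracy. That rests on the combined figure of 94/95 in the Results.

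The Conclusion section reads: "Ultrasonography and waveform capnography are equally reliable and accurate methods of confirming endotracheal tube position". The first Recommendation says ultrasound "can be used as an alternate method of confirming endotracheal tube position in operating theatres". The aim in the Abstract's Background was to see whether ultrasound could become routine alongside capnography.

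**The concern.** A claim that two tests are equal needs either a margin within which they count as equal, or a measure on which a tie means something for the purpose at hand. Overall accuracy is not such a measure here. It treats a tube left in the oesophagus and a false alarm on a tracheal tube as the same loss, although the Introduction names oesophageal intubation as a source of serious morbidity and mortality. It also shifts with the proportion of tubes that are tracheal.

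Overlapping intervals do not fill the gap. They show that no difference was established, which is a weak finding when specificity rests on 11 tubes.

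At stake are the main Conclusion, the claim that the combination increases precision, and the support for the first Recommendation.

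**Working it through.** **Inputs (Tables 8 and 9).** Ultrasound: TP 82, FP 1, FN 2, TN 10. Capnography: TP 81, FP 0, FN 3, TN 11. In total 84 tubes were tracheal and 11 oesophageal. A false positive is an oesophageal tube called tracheal.

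**1. Reproduce the stated figure.** Ultrasound (82+10)/95 = 92/95 = 96.84%. Capnography (81+11)/95 = 92/95 = 96.84%. Both agree with the Abstract.

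**2. Dependence on case mix.** With tracheal share t, accuracy = t × sensitivity + (1−t) × specificity. Sensitivities are 82/84 and 81/84; specificities are 10/11 and 11/11. The two lines cross at t = (1/11) / (1/11 + 1/84) = 84/(84+11) = 84/95, which is the share in this sample. The Discussion cites oesophageal rates below 2% in elective work ("Reported incidence of oesophageal intubations during elective intubation is less than 2"%) and 6-16% in in-hospital emergencies. Holding the observed sensitivity and specificity fixed:

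- 2% oesophageal: ultrasound 0.98×0.9762 + 0.02×0.9091 = 97.5%; capnography 0.98×0.9643 + 0.02 = 96.5%.
- 6%: ultrasound 97.2%; capnography 96.6%.
- 16%: ultrasound 0.84×0.9762 + 0.16×0.9091 = 96.5%; capnography 0.84×0.9643 + 0.16 = 97.0%.

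The order reverses within the document's own range of rates.

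**3. Dependence on error weight.** If an accepted oesophageal tube counts w times a false alarm, the loss is 2+w for ultrasound and 3 for capnography. The documents give no w, so this is an assumed range: w=1 gives 3 vs 3; w=2, 4 vs 3; w=5, 7 vs 3; w=10, 12 vs 3. In this sample the tie needs w=1.

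**4. The two error rates, with exact (Clopper-Pearson) 95% intervals.**

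- Oesophageal tube accepted: ultrasound 1/11 = 9.1% (0.2-41.3); capnography 0/11 = 0% (0-28.5).
- Tracheal tube rejected: ultrasound 2/84 = 2.4% (0.3-8.3); capnography 3/84 = 3.6% (0.7-10.1).

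**5. Paired comparison.** The Results say every tracheal tube was correctly read by at least one method, so the 2 and 3 false negatives are different patients. Capnography rejected the oesophageal tube that ultrasound accepted. The discordant pairs are therefore 3 against 3: exact McNemar p = 1.0, accuracy difference 0 with a Wald 95% interval of about ±5.1 points. For specificity, ultrasound minus capnography is −9.1 points, with an approximate paired Newcombe interval of −38 to +18 points.

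**6. The combined figure.** The Results credit a tracheal tube as correct if either method said trachea, and report 10 of the 11 oesophageal tubes as identified by both together. That amounts to a rule of calling trachea when either method does:

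- Sensitivity 84/84 (exact lower limit 0.025^(1/84) = 95.7%).
- Specificity 10/11 = 90.9% (58.7-99.8).
- Accuracy (84+10)/95 = 94/95 = 98.9%.

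Against capnography alone, accuracy rises by 2/95. Three false alarms are removed and one accepted oesophageal tube is added, so specificity falls from 11/11 to 10/11.

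**The case against.** The strongest reply is that the paper does not rest on the accuracy tie. The Discussion argues from sensitivity, specificity, PPV and NPV with their intervals. Accuracy is not among the five specific objectives, and Table 10 lists it after those four measures. This stands. A reader might infer that accuracy is the sole basis for the Conclusion, and the documents do not support that.

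A reader might also infer that the tie conceals the difference in error type. It does not. The Abstract gives both specificities with intervals immediately after the accuracy figure, the Results state the accepted oesophageal tube in words, and the Discussion examines that case. The exact intervals in step 4 are the complements of those already printed.

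The Abstract's own conclusion is milder: it calls both methods reliable and accurate without 'equally', and favours using them together. The Discussion also asks for a third method when the two disagree. These points stand and narrow the problem to particular sentences.

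They do not rescue those sentences. No margin was set. The sample size aimed at a 5-point margin of error on specificity, yet the ultrasound interval runs from 58.72% to 99.77%. Intervals that wide are compatible with equality and with a large difference.

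**Conclusion.** The concern holds for the word 'equally' in the Conclusion and the Discussion, and for the unqualified claim that the combination increases precision. On the safety-relevant error the data show neither a difference nor equality: 1/11 against 0/11, with a paired interval of roughly −38 to +18 points.

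A reader might infer that ultrasound is the less safe method. That is not supported either, because the specificity gap is one patient.

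The error rates in step 4 need only Tables 8 and 9. The case-mix figures assume that the observed sensitivity and specificity carry over to other settings. The paired results and the 84/84 assume the Results sentence about tracheal tubes is right. The paired table it implies (79 both trachea, 4 ultrasound only, 2 capnography only, 10 both oesophagus) gives kappa 0.733 against the stated 0.749, so that sentence should be checked against the data.

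This should be fixed. It concerns what is concluded, not the counts themselves.

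**What to change.** 1. Delete 'equally' in the Conclusion and in the Discussion under Ultrasonography vs Capnography, and state that equality was not shown.
2. Lead the comparison with oesophageal tubes accepted (1/11 vs 0/11) and tracheal tubes rejected (2/84 vs 3/84), with the exact intervals.
3. Keep overall accuracy as a secondary figure, labelled as dependent on case mix and on equal weighting of errors.
4. In the Results, report the combination by its sensitivity (84/84) and specificity (10/11), and name the rule it implies. Wherever the gain in precision is claimed (Abstract, Discussion, Conclusion), say that it came from fewer false alarms and that specificity was below capnography's 11/11.
5. Reconcile the first Recommendation, which presents ultrasound as an alternate method, with the Abstract's aim of use alongside capnography. Which wording to keep is for the investigators.

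The cost is rewording and one small table from counts already reported. The drawback for the authors is a less favourable conclusion.
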